#### 10.4 Statistical Analyses

Individual and mean concentration versus time curves will be presented using linear and semi-log scales for leuprolide acetate. Descriptive statistics (mean, standard deviation, coefficient of variation, median, minimum value, maximum value and geometric mean) of the serum concentrations versus time will be presented. Summaries of the leuprolide concentrations will also be reported for each intermediate (within the 28-day dosing interval) and for each follow-up (post-dosing period) visit.

The summaries will be provided for all PK parameters listed above. The most important PK endpoint for the oral groups is  $C_{ss\_oral}$ . A related primary endpoint for the Lupron group is  $C_{ss\_im}$ . No formal statistical between-treatment comparisons are planned.

For Treatment “D” leuprolide concentration levels will be summarized for individual sampling timepoints.

## 11. Pharmacodynamics Analyses

Shells for all summary descriptive statistic tables and listings referred to in this section are displayed in the document containing the TFL shells; the shells may be revised as they are presented to illustrate the general layout of data to be included in the final report.

The primary statistical analyses of PD data will be conducted on the primary PD population. Supportive statistical analyses of PD data will be conducted on the supportive PD population.

### 11.1 Pharmacodynamic Concentration and Parameters

A total of 11 PD blood samples for Treatments “A” and “B” and 10 PD blood samples for Treatment “C” will be taken for the determination of LH, FSH, E2, and progesterone levels. Serum concentrations of PD endpoints will be measured at screening and in the morning (in the Ovarest™ groups, just prior to oral dosing) on Dosing period Treatment Days 1, 8, 15, 22 and 28 (except for Treatment “C”), and in the morning of Evaluation Period Days 1 (or Day 29), 7, 14, 21 and 28.

A total of 10 PD blood samples for Treatment “D” will be taken for the determination of LH, FSH, E2, and progesterone levels. Serum concentrations of PD endpoints will be measured at screening and in the morning just prior to oral dosing) on Dosing period Treatment Days 1, 8, 15, 22, and in the morning of Evaluation Period Days 1 (or Day 29), 7, 14, 21 and 28.

The primary PD metric - suppression of E2 level - will be assessed at each on-treatment (28-day dosing) and 28-day post-dosing evaluation timepoint. Treatment dosing Day 22 and Treatment dosing Day 29 evaluations (separately and combined) will be considered as most important primary evaluations.

For the purposes of the statistical analyses, PD measurements for Day 29 will be considered as the last measurements of the 28-day dosing interval. This Day 29 measurement will NOT be included in the post-dosing PD evaluations. The post-dosing PD evaluations will utilize measurements collected on post-dosing days 7, 14, 21, and 28.

Suppression of E2 levels across various evaluation intervals (e.g., Days 22-29 of the dosing period, entire 28-day dosing period, and 28-day postdosing period) will be evaluated in two ways:

- (1) E2 level is considered suppressed during the evaluation period if a value below pre-specified threshold was reported **at least once** during that period. For example, if a subject had E2 ≤40 pg/mL at Day 29 and E2 > 40 pg/mL at Day 22, she will be categorized as a subject with a suppressed E2 level during the 22-29 Day evaluation period;
- (2) E2 level is considered suppressed during the evaluation period if a value below pre-specified threshold was reported **at each timepoint of that period**. For example, if a

subject had  $E_2 \leq 40$  pg/mL at Day 29 and  $E_2 > 40$  pg/mL at Day 22, she will not be categorized as a subject with a suppressed  $E_2$  level during the 22-29 Day evaluation period; To be considered as a subject with a suppressed  $E_2$  level during that period,  $E_2$  must be  $\leq 40$  pg/mL on both Days 22 and 29.

The former definition, (1) will be considered as primary.

Note: For Treatments “A” and “B” additional protocol-specified evaluations will be performed for Days 22 and 28 of the dosing period

Similar approach will be utilized for other PD endpoints (e.g., a suppression of ovulation as evidence by progesterone level – see below).

In addition to a primary  $E_2$  suppression threshold ( $E_2 \leq 40$  pg/mL), a suppression of  $E_2 \leq 20$  pg/mL,  $\leq 50$  pg/mL,  $\leq 60$  pg/mL, and  $\leq 70$  pg/mL may also be assessed, if considered necessary. .

The suppression of ovulation (as evidenced by progesterone levels  $< 3$  ng/mL) will be assessed at each on-treatment (28-day dosing) and 28-day post-dosing evaluation timepoint. Treatment dosing Day 22 and Treatment dosing Day 28 (Day 29 for Treatments “C” and “D”) evaluations (separately and combined) will be considered as most important (primary) evaluations.

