	
PK/PD data for Lupron Depot® 3.75-mg and Lupron Depot® 11.25-mg (3-month) formulations.
 
The most important objective of this study is to provide adequate PD assessments to support development of the Leuprolide Oral Tablet with estradiol (E2) suppression similar to those reported for the Lupron Depot® and other E2-inhibiting hormonal therapies. Another reason for this trial is to describe the PK/PD dose-proportionality of the 4-mg and 10-mg Leuprolide Oral Tablet administered as qd and/or bid regimens.
 
Thus, the Primary Study Objectives are:
 
 
1) To determine the safety and to provide comparative evaluation of the PK and PD profiles of the 4-mg Leuprolide Oral Tablets following qd and bid administration and the 10-mg Leuprolide Oral Tablets following bid administration in healthy, premenopausal female volunteers over 28 days vs a marketed formulation of leuprolide acetate administered IM for one month of therapy.
 
2) To evaluate the PK properties of Leuprolide Oral Tablets after multiple dosing (ie, 28 days of dosing)
 
3) To assess the PK/PD dose-proportionality of the Leuprolide Oral Tablets administered as 4 mg qd, 4 mg bid and 10 mg bid dosing regimens
 
4) To evaluate the PK and/or PD properties of the Leuprolide Oral Tablets (eg, E2 suppression rates) vs other hormonal therapies for the treatment of reproductive disorders, including endometriosis.
 
 
Secondary Study Objective:
 
To evaluate safety and tolerability of the long-term administration of leuprolide in healthy female volunteers.

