Statistical Methods	
The primary statistical analyses of PK data (Treatments “A” and “B” only) will be conducted on the population of subjects completing 28 days of dosing. Supporting evaluations will be performed for the cohort of subjects who received

	
at least one dose of study medication and provided any PK data.
 
Similarly, the primary statistical analyses of PD data (all Treatment groups) will be conducted on the population of subjects completing 28 days of dosing. Supporting evaluations will be performed for the cohort of subjects who received at least one dose of study medication and provided any PD data.
 
The safety analysis will be performed on all subjects who received at least one dose of study medication.
 
Incidence of subjects with suppressed E2 levels will be reported for each study period by treatment group. The incidence of subjects with suppressed E2 levels for the fourth treatment week (Day 22 and Day 29 combined) will be considered as a primary efficacy endpoint. The incidence of suppressed ovulation during the same period will also be reported. The FSH, LH, E2 and progesterone levels will be reported by treatment group for each evaluation period by using summary statistics. Changes in these parameters from prestudy baseline will also be summarized by treatment group.
 
The summaries will be provided for the PK parameters with a focus on steady-state concentration levels. PD and PK parameters will be graphed by treatment group for each evaluation period. Correlations between leuprolide concentration levels and PD parameters will be assessed.
 
Safety endpoints, study discontinuation information, changes in the physical and gynecological examination findings, and treatment-emergent changes in vital signs and clinical laboratory test results will be summarized. The subject incidence of TEAEs will be reported by the treatment received.
 
A detailed Statistical Analysis Plan will be developed prior to the database lock.

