### 12.3 Pharmacodynamic Parameters and Analyses

As noted earlier, PD assessments (LH, FSH, E2, and progesterone) will be performed during the Screening Visit and immediately prior to dosing on Treatment Days 1, 8, 15, 22, and 29. Additional PD assessments will be performed during the follow-up visits (postdosing Days 7, 14, 21 and 28).

The primary PD metric - suppression of E2 level - will be assessed at each on-treatment evaluation timepoint. Treatment Day 22 and Treatment Day 28 evaluations (separately and combined) will be considered as most important. The summaries will also be provided across the entire dosing period and the entire postdosing period, separately and combined. The summaries of PD metrics may be further stratified by the cycle period (days) of the start of dosing.

In addition to a primary E2 suppression threshold (E2 ≤40 pg/mL), a suppression of E2 below 20 pg/mL may also be assessed, if considered necessary. The suppression of ovulation (as evidenced by progesterone levels <3 ng/mL) will be evaluated with Treatment Day 22 and Postdosing Day 1 assessments positioned as primary. Changes from predosing baseline in E2 and progesterone levels will also be summarized at each on-treatment evaluation timepoint. Predosing baseline for all PD metrics is the highest value across two observations: (a) screening measurement and (b) measurement taken just prior to the first dose of the study drug. Similar summaries will be provided for the follow-up visits (postdosing Days 7, 14, 21, and 28). In addition, time to return to prestudy baseline hormonal levels could be estimated.

PD parameters will be graphed by treatment group for each evaluation period.

Additionally, correlations between leuprolide concentration levels and PD parameters will be examined.

Number of vaginal (menstrual) bleeding days will be summarized by treatment group for 28 days of therapy and for 28 days of poststudy follow-up. The subject incidence of the onset of menstrual period after completion of therapy will be reported for each treatment group.

Further details of the PD data analysis will be disclosed in the SAP.

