**25. APPENDIX G: ACCEPTABLE DAYS FOR INITIATION OF DOSING IN RELATION TO CYCLE LENGTH**

Cycle Length (days)	Acceptable days for initiation of dosing		
21	Day 1 – Day 4	-or-	Day 11 to Day 21
22	Day 1 – Day 4	-or-	Day 12 to Day 22
23	Day 1 – Day 4	-or-	Day 13 to Day 23
24	Day 1 – Day 4	-or-	Day 14 to Day 24
25	Day 1 – Day 4	-or-	Day 15 to Day 25
26	Day 1 – Day 4	-or-	Day 16 to Day 26
27	Day 1 – Day 4	-or-	Day 17 to Day 27
28	Day 1 – Day 4	-or-	Day 18 to Day 28
29	Day 1 – Day 4	-or-	Day 19 to Day 29
30	Day 1 – Day 4	-or-	Day 20 to Day 30
31	Day 1 – Day 4	-or-	Day 21 to Day 31
32	Day 1 – Day 4	-or-	Day 22 to Day 32
33	Day 1 – Day 4	-or-	Day 23 to Day 33
34	Day 1 – Day 4	-or-	Day 24 to Day 34
35	Day 1 – Day 4	-or-	Day 25 to Day 35

Note: Subjects enrolled to the third oral dose (Treatment “D”) will have a dosing initiation visit scheduled 5-9 days before the anticipated start of their next menstrual cycle, based on their self-reported menstrual cycle length and the day the current menstrual cycle began.

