## 11.2 Statistical Analyses

Individual and mean concentration of hormonal levels versus nominal time curves will be presented by treatment group for each evaluation timepoint. Descriptive statistics (sample size “n”, mean, standard deviation, coefficient of variation, median, minimum value and maximum value) of hormonal levels will be presented for each timepoint.

Summaries of the LH, FSH,  $E_2$ , and progesterone levels will be reported for each dosing and post-dosing evaluation timepoint, for the dosing days 22 and 28 (Day 29 for Treatments “C” and “D”) (combined: i.e. the maximum among the 2 values) and, optionally, for the entire 28-day dosing period and the entire post-dosing Evaluation Period. Changes from pre-dosing baseline in LH, FSH,  $E_2$  and progesterone levels will also be summarized (sample size “n”, mean, standard deviation, median, minimum value and maximum value) at each on-treatment evaluation timepoint. Pre-dosing baseline for all PD metrics is the highest value across two observations: (a) screening measurement and (b) measurement taken just prior to the first dose of the study drug. Similar summaries will be provided for the follow-up visits (postdosing Days 7, 14, 21, and 28). In addition, time to return to pre-study baseline hormonal levels could be estimated.

Summaries of PD metrics may be further stratified by the cycle period (days) of the start of dosing. Categorical variables will be summarized by using frequency counts and percentages for each treatment by visits involved. In addition, the number of patients with missing values will be displayed.

Additionally, correlations between leuprolide concentration levels and PD parameters will be examined graphically. PD parameters may include LS, FSH, E2 and progesterone levels. These evaluations will not be performed for Treatment “D”.

Number of vaginal (menstrual) bleeding days will be summarized by treatment group for 28 days of therapy and for 28 days of post-study follow-up. The subject incidence of the onset of menstrual period after completion of therapy will be reported for each treatment group.

The onset of menstrual period is defined as at least three consecutive bleeding/spotting days during the 28-day postdosing period.

Additional PD analyses could be performed if necessary.

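### The primary combined E2 rule counts a woman as suppressed on one low sample of two; the stricter rule, already planned, should carry the primary label, on the same days as the combined E2 level.

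*SAP*

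**What the plan says.** The protocol synopsis (Statistical Methods) states that the incidence of suppressed E2 "for the fourth treatment week (Day 22 and Day 29 combined) will be considered as a primary efficacy endpoint". Protocol 12.3 sets the primary threshold at E2 ≤40 pg/mL. Neither place says whether a woman must meet it on one day or on both.

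SAP 11.1 supplies the definition. Under rule (1), E2 counts as suppressed over an interval "if a value below pre-specified threshold was reported at least once during that period". Under rule (2), the value must meet the threshold at every timepoint of the interval. The SAP's own example is a woman above 40 pg/mL on Day 22 and at or below 40 on Day 29: suppressed under (1), not under (2). It then states: "The former definition, (1) will be considered as primary". The intervals named are Days 22-29, the whole dosing period and the 28-day postdosing period. A similar approach is extended to other PD endpoints, including progesterone. The Day 22 and Day 29 results are also to be reported separately.

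SAP 11.2 summarises the hormone levels for the fourth week as "combined: i.e. the maximum among the 2 values". There the two days are 22 and 28 for Treatments A and B, and 22 and 29 for C and D.

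**The concern.** Rule (1) asks whether the lower of two values reached the threshold. The subjects are healthy women with regular cycles, sampled once a week, so a single low value may reflect where a woman is in her cycle. There is no untreated arm to show how often that happens, and stratification by cycle day at the start of dosing is only optional (SAP 11.2).

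The protocol synopsis says: "The most important objective of this study is to provide adequate PD assessments to support development of the Leuprolide Oral Tablet with estradiol" suppression similar to that reported for Lupron Depot. No inferential analysis is planned, and the arms are small (9, 9 and 5 women in A, B and C, and up to 12 in D). The rate labelled primary is therefore what most readers will take away. A lenient rule can add responders only among women who are not suppressed throughout, so it favours a weakly suppressing regimen over a strongly suppressing one. In the postdosing interval, the same rule can describe a woman who is cycling as suppressed.

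A second problem is that the responder status follows the minimum of two values and the tabulated combined level follows the maximum.

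**Working it through.** The documents state no expected rate, power or error rate for this endpoint, so there is no figure to reproduce. Three checks were made.

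**1. Logic of the two outputs.** Rule (1) is min(Day 22, Day 29) ≤40. Rule (2) is max(Day 22, Day 29) ≤40. An illustrative woman with 90 pg/mL on Day 22 and 30 on Day 29 is a responder under (1), since min = 30, and a non-responder under (2), since max = 90. In C or D her combined E2 level in SAP 11.2 would be 90, although she is a primary responder. In A or B the level would use Day 28 in place of Day 29, so status and level do not even rest on the same samples.

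**2. Calendar.** Inputs from the documents:
- cycle length L = 21 to 35 days (Protocol 8.1);
- start on cycle days 1-4 or in the last 11 days of the cycle for A-C (Protocol synopsis and Appendix G);
- start 5-9 days before the expected menses for D (Protocol 7.1);
- samples on Treatment Days 8, 15, 22 and 29, and on postdosing Days 7, 14, 21 and 28, which are Treatment Days 35, 42, 49 and 56.

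Assumptions not in the documents: the cycle runs on unaltered, and undrugged E2 is ≤40 pg/mL on cycle days 1-4 (varied from 1-3 to 1-6).

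For a start on cycle day s, the cycle day on Treatment Day d is ((s + d − 2) mod L) + 1. For D, s = L + 1 − k with k = 5 to 9. The number of combinations is 4 × 15 = 60 for early-start A-C, 11 × 15 = 165 for late-start A-C, and 5 × 15 = 75 for D.

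Example with L = 28: starts on cycle days 1-4 put Day 22 on cycle days 22-25 and Day 29 on cycle days 1-4, in all four cases. None of the 11 late starts puts either day in the window. For D, Day 22 falls on cycle days 13-17 and Day 29 on cycle days 20-24, so 0 of 5.

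Over all cycle lengths, for Days 22 and 29:

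| Group | Either day in window 1-4 | Range, windows 1-3 to 1-6 | Both days |
|---|---|---|---|
| A-C, early start | 26/60 (43%) | 21-34 | 0 |
| A-C, late start | 22/165 (13%) | 18-27 | 0 |
| A-C, all | 48/225 (21%) | 39-61 | 0 |
| D | 6/75 (8%) | 6 throughout | 0 |

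The six D combinations come from cycles of 21 days (three), 22 days (two) and 23 days (one). The zeros are structural: samples seven days apart cannot both fall in a window of up to seven days when cycles last at least 21 days.

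For D over the longer intervals, at least one of the four samples falls in the window for 45/75 combinations in the dosing period and for 47/75 (63%; range 38-65) in the postdosing period. None has all four.

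**3. Leniency apart from menses.** Let p be the chance that one sample is ≤40 without drug effect, with independent samples (both assumed). Rule (1) scores 1 − (1 − p)² and rule (2) scores p².

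| p | Rule (1) | Rule (2) |
|---|---|---|
| 0.10 | 19% | 1% |
| 0.20 | 36% | 4% |
| 0.30 | 51% | 9% |

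At p = 0.20 in 12 women, that is 12 × 0.36 = 4.3 expected false responders against 12 × 0.04 = 0.5.

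**The case against.** The strongest reply is that the harm is already limited. Rule (2) is specified in advance with a worked example, the Day 22 and Day 29 rates stand beside the combined one as primary evaluations, and no decision rule depends on the combined rate. This stands, and it lowers the severity. It does not explain why the weaker rule carries the label, and the SAP gives no reason.

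A second reply is that the size rests on outside assumptions. This also stands: no passage gives E2 by cycle day, p is assumed, and the grid gives a 21-day cycle the same weight as a 28-day one.

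A third is that Lupron Depot's label (Protocol Appendix D) says E2 may rise in the first weeks before it falls, so crediting a woman who first reaches the threshold on Day 29 is arguable in a 28-day study. That is a fair reason to report rule (1), and the separate Day 29 rate already gives her credit.

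Four stronger readings are tempting and are not supported:
- **Menses inflates the fourth-week rate in every oral arm.** In D the exposure is 6/75, and nil for a 28-day cycle.
- **SAP 11.1 and 11.2 contradict each other.** One classifies responders and the other summarises levels. They are unreconciled conventions.
- **Recovery would be hidden.** The 47/75 assumes no drug effect on the calendar at all, and postdosing E2 by visit and onset of menses are reported as well.
- **The lenient rule was chosen because of the data.** A preliminary look at PK and PD results preceded the amendment on which the SAP is based (SAP 1 and 7), but nothing links the two.

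**Conclusion.** The point holds in a limited form. The primary combined rule can be met by one low sample, and in cycling women without an untreated arm such a sample need not reflect drug effect. If E2 is ≤40 pg/mL on cycle days 1-4 of an unaltered cycle, a fourth-week sample falls there in 21% of permitted combinations for A-C (43% for early starts, 13% for late starts) and in 8% for D. Any inflation therefore differs by arm and start window, and is slight for D on the primary endpoint. The percentages are shares of combinations, and the documents do not say how many women fall in each. The every-sample rule cannot be met by menses alone.

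The mismatch between status and level, including the different day pair for A and B, needs no assumption: it is in the text. A reader might infer that the primary result is unusable. The descriptive analysis and the planned stricter and single-day rates do not support that. This should be fixed, but it is not a fatal fault.

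**What to change.** In SAP 11.1, make rule (2), E2 ≤40 pg/mL on both Day 22 and Day 29, the primary combined rule in every arm, and report rule (1) as supportive. In SAP 11.2, use Days 22 and 29 for the combined E2 level in A and B as well. The primary status is then the same as a combined level ≤40. The Day 22/28 summary for A and B can stay as an additional one.

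For the whole dosing and postdosing intervals, report the every-sample rate and the number of visits with E2 ≤40 for each woman, in place of the one-sample rule as primary. State how a woman with one of the two fourth-week samples missing is classified, since SAP 13 allows no imputation and rule (2) needs both.

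The cost is SAP wording and minor table changes, as both rules are already planned. The headline rate can only fall or stay the same, and a woman who first reaches the threshold on Day 29 is no longer a combined responder. She remains in the separate Day 29 rate and in the supportive analysis.

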#### **4. Changes from the Protocol**

Any changes in planned analyses compared to the protocol will be noted in this section.

Primary statistical analyses of the PD endpoints will utilize measurements for Treatment Day 22 and Treatment Day 29 (not Treatment Day 28 as noted in the protocol). This change will ensure consistent methodology across all treatment groups some of which (Treatments "C" and "D") did not have scheduled PD assessments on Treatment Day 28.

Suppression of  $E_2 \leq 50$  pg/mL,  $\leq 60$  pg/mL, and  $\leq 70$  pg/mL may also be assessed, if considered necessary.

The determination of the suppression of  $E_2$  or other PD endpoints across evaluation intervals was clarified.

An additional analysis for the adverse drug reactions (ADR) (excluding the PT “Menstrual Disorder”) was described.

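### Ovulation suppression appears to inherit the at-least-once rule written for E2, so a woman with progesterone ≥3 ng/mL on one primary day can still count as suppressed; Day 28 is also used for A/B against SAP Section 4

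*SAP*

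**What the plan says.** **Combining rule.** SAP 11.1 gives two rules for E2 across an evaluation interval. Rule (1) counts a subject as suppressed if she meets the threshold at least once; rule (2) requires it at every timepoint. On their ranking: "The former definition, (1) will be considered as primary". It then extends this: "Similar approach will be utilized for other PD endpoints (e.g., a suppression of ovulation as evidence by progesterone level". The ovulation paragraph that follows sets the criterion (progesterone <3 ng/mL) and names its two primary days, separately and combined, but gives no combining rule of its own.

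SAP 11.2, summarising hormone levels over the same two days, takes "combined: i.e. the maximum among the 2 values".

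The protocol synopsis (Statistical Methods) defines E2 suppression for the fourth treatment week as Days 22 and 29 combined, then adds: "The incidence of suppressed ovulation during the same period will also be reported".

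**Days.** SAP Section 4: "Primary statistical analyses of the PD endpoints will utilize measurements for Treatment Day 22 and Treatment Day 29 (not Treatment Day 28", with consistency across arms as the reason. Protocol 12.3 says ovulation suppression "will be evaluated with Treatment Day 22 and Postdosing Day 1 assessments positioned as primary"; Postdosing Day 1 is Day 29. The ovulation paragraph of SAP 11.1 nevertheless reads "Treatment dosing Day 22 and Treatment dosing Day 28 (Day 29 for Treatments" C and D), and SAP 11.2 reads "for the dosing days 22 and 28 (Day 29 for Treatments" C and D).

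**The concern.** The two endpoints are not symmetric. Under the plan's own criterion, progesterone ≥3 ng/mL is evidence that ovulation was not suppressed. A low value is weaker evidence the other way, because untreated women also have low progesterone before ovulation and around menses. With two samples a week apart, rule (1) lets one low sample override a high one, and only a woman with ≥3 ng/mL on both days is counted as not suppressed.

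The combined rate is one the synopsis says will be reported, and SAP 11.1 ranks it among the primary evaluations. If an inactive regimen would score high on it, a reader could take that rate as evidence of ovulation suppression.

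The day labels are a second, smaller matter. As written, A and B are judged on a different second day from C and D, which is what Section 4 set out to prevent.

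**Working it through.** The documents state no figure to reproduce, so the check has three parts.

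**1. Applying the text to one woman.** Progesterone is 1 ng/mL on Day 22 and 12 ng/mL on Day 29.

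| Rule | Result |
|---|---|
| SAP 11.1 rule (1), at least once | suppressed |
| SAP 11.1 rule (2), every timepoint | not suppressed |
| SAP 11.2, maximum = 12 | ≥3 ng/mL, agrees with rule (2) |

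A maximum <3 holds exactly when both values are <3, so the 11.2 combination corresponds to rule (2).

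**2. What an arm with no drug effect would score.**

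From the documents: A/B/C start on cycle days 1-4 or in the last 11 days of the cycle (days 18-28 of a 28-day cycle), giving 15 start days; D starts 5-9 days before the next menses (cycle days 20-24).

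Assumptions, not in the documents: progesterone is ≥3 ng/mL for L = 8, 10 or 12 days, the last such day falls 2 days before menses, and start days are equally weighted.

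For start day s and cycle length C, the cycle day on treatment day d is ((s−1)+(d−1)) mod C + 1. Progesterone is high on cycle days C−2−L+1 to C−2.

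Central case, C = 28 and L = 10, high on cycle days 17-26:

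- Starts 1-4: Day 22 falls on cycle days 22-25 (high), Day 29 on 1-4 (low). Rule (1) counts 4 of 4.
- Starts 18-28: Day 22 falls on 11-21, low for starts 18-23 (6). Day 29 falls on 18-28, low for starts 27-28 (2). Rule (1) counts 8 of 11.
- Total: rule (1) 12/15 = 80%. No start is low on both days, so rule (2) is 0/15.

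| C = 28, scored suppressed | L = 8 | L = 10 | L = 12 |
|---|---|---|---|
| A/B/C, Days 22+29, rule (1) | 14/15 (93%) | 12/15 (80%) | 10/15 (67%) |
| A/B/C, Days 22+29, rule (2) | 1/15 (7%) | 0/15 | 0/15 |
| A/B/C, Day 22 alone | 8/15 (53%) | 6/15 (40%) | 4/15 (27%) |
| A/B/C, Day 29 alone | 7/15 (47%) | 6/15 (40%) | 6/15 (40%) |
| D, Days 22+29, rule (1) | 5/5 | 4/5 | 2/5 |
| A/B/C, Days 22+28, rule (1) | 13/15 (87%) | 11/15 (73%) | 9/15 (60%) |

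Sensitivity:

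- High window ending 1 or 3 days before menses: A/B/C rule (1) is unchanged at 93/80/67%; rule (2) is 13/0/0% or 0/0/0%. D rule (1) moves to 100/100/60% or 100/60/20%.
- Cycle lengths 21-35 days, equally weighted, across start groups: rule (1) 67-94%, rule (2) 4-30%.
- Whole dosing period (Days 8, 15, 22, 29) or post-dosing period (postdosing Days 7, 14, 21, 28): rule (1) gives 100%; rule (2) gives 0% for 28-day cycles.

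For 9 subjects (A or B), the central case is 0.80 × 9 = 7.2, about 7 of 9, against 0 of 9. Using Day 28 changes this to 11/15 × 9 = 6.6, a difference of 0.6 of a subject.

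**3. The same direction without a cycle model.** Let q be the chance of a low value on one day and ρ the between-day correlation; both are assumed. Rule (1) = q + q(1−q)(1−ρ) and rule (2) = q − q(1−q)(1−ρ). At q = 0.5: 75% against 25% (ρ = 0), or 62.5% against 37.5% (ρ = 0.5). At q = 0.8: 96% against 64%, or 88% against 72%. Each woman who is high on exactly one of the two days moves an arm's rate by 1/12 = 8.3, 1/9 = 11.1 or 1/5 = 20 points for n = 12, 9 or 5.

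**The case against.** **The reading is not forced.** The SAP says only that a similar approach applies, and the sentence making rule (1) primary sits in the E2 text. The maximum in 11.2 covers progesterone on the same pair of days and could be the intended meaning of combined; that would already be rule (2). This stands in part: rule (1) is the natural reading, not an explicit statement. But 11.2 summarises hormone levels and does not classify subjects, and if it is the intended definition the SAP still has to say so.

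**The maximum conflicts with E2 as well.** True. For E2, however, the primary classification rule is explicit; for ovulation it is not.

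**The illustration depends on pooling and timing.** Also fair. In the 28-day model, rule (1) equals Day 29 alone for days 1-4 starters and Day 22 alone for D, so it adds nothing to the better single day in those groups. Only late starters show inflation within a group, from 6/11 to 8/11 in the central case. D ranges from 20% to 100% as the window moves. The early/late split is unknown, and the trial has no untreated arm. These points qualify the size, not the direction.

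**The consequence is small.** E2 suppression is the primary efficacy endpoint, no inferential analyses are planned, and single-day rates, rule (2) and individual curves remain available. This limits the severity.

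**Conclusion.** The concern holds. As written, the combined ovulation rate can count a woman as suppressed on one low sample despite a high one. Assuming no drug effect, 28-day cycles, a high-progesterone phase of 8-12 days ending 2 days before menses and equally weighted start days, rule (1) would score 67-93% of A/B/C and 40-100% of D as suppressed on Days 22 and 29, and 100% over either full period. These are benchmarks for an inactive arm, not predictions for any trial arm. They show that the rule (1) ovulation rates carry little information. Rule (2) is much better but not error-free: 4-30% in the same model across cycle lengths 21-35 days.

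The Day 28 label is a plain contradiction of SAP Section 4, Protocol 12.3 and the synopsis. Its effect is one start day in 15, less than one subject of 9. The whole point should be fixed, but it does not threaten the E2 result.

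**What to change.** In SAP 11.1, state that for suppression of ovulation the primary interval definition is (2): progesterone <3 ng/mL at every sampled timepoint of the interval. Keep definition (1) for ovulation, if at all, as supportive only. This also agrees with the maximum in 11.2.

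In the ovulation paragraph of 11.1 and the combined summaries of 11.2, use Day 29 for all arms. Keep Day 28 for A and B as the additional evaluation that 11.1 already describes.

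The cost is one sentence and two day labels. Day 29 is sampled in every arm, so no new data are needed. Reported ovulation-suppression rates will be lower, the ovulation rule will differ from the E2 rule, and an ovulation falling between samples can still be missed. PD results for A, B and C were reviewed before Treatment D was added (SAP Section 7), so the change should be recorded as made after that review.
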